1. LIST OF ABBREVIATIONS

AT	As-treated analysis
ATC	Anatomical Therapeutic Chemical Classification System
AvoHILMO	Register of primary health care visits
BI	Boehringer Ingelheim International GmbH
BMI	Body mass index
CI	Confidence interval
COPD	Chronic obstructive pulmonary disease
CPRD	Clinical Practice Research Datalink
CV	Cardiovascular
DDD	Defined daily dose
DPP-4	Dipeptidyl peptidase-4
eGFR	Estimated glomerular filtration rate
EMA	European Medicines Agency
EMR	Electronic medical record
ENCePP	European Network of Centres for Pharmacoepidemiology and Pharmacovigilance
EU	European Union
FDA	Food and Drug Administration
GLP-1	Glucagon-like peptide-1
GP	General practitioner
GPP	Good Pharmacoepidemiology Practices
GPV	Good Pharmacovigilance Practices
HbA1c	Glycated haemoglobin A1c
HES	Hospital Episode Statistics
HF	Heart failure
HILMO	Care register for health care
HR	Hazard ratio
HUS	Helsinki University Hospital region
ICD-10	International classification of diseases
IPTW	Inverse-probability of treatment weights

ITT	Intention-to-treat analysis
MI	Myocardial infarction
MSM	Marginal structural model
NCC	Nested case-control
NHS	National Health Service
██████████	██████████
NSAID	Non-steroidal anti-inflammatory drugs
ONS	Office for National Statistics
PASS	Post-safety study
PH	Proportional hazards
PID	Personal identification number
PS	Propensity score
PSUR	Periodic Safety Update Report
PY	Person-years
RMP	Risk management plan
RR	Relative risk
SEAP	Statistical/Epidemiological Analysis Plan
SGLT-2	Sodium glucose co-transporter-2
SID	Study identification number
SIR	Standardized incidence ratio
T2D	Type 2 diabetes mellitus
THIN	The Health Improvement Network database
UK	United Kingdom
US	United States
UT	Urinary tract
UTI	Urinary tract infection

3. ABSTRACT

Name of company: Boehringer Ingelheim			
Name of the finished medicinal product: Jardiance®, Synjardy			
Name of active ingredient: Empagliflozin (A10BK03) Metformin and empagliflozin (A10BD20)			
Protocol date: 16-Sep-2015	Study number/ Document number: 1245.97 / c03856813-10	Version/Revision: 8.0	Version/Revision date: 17-May-2023
Title of study:	Post-authorisation safety study to assess the risk of urinary tract malignancies in relation to empagliflozin exposure in patients with type 2 diabetes: a multi-database European study		
Rationale and background:	
Empagliflozin is an oral blood glucose lowering drug belonging to the sodium glucose co-transporter-2 (SGLT-2) inhibitor class. SGLT-2 inhibitors promote the renal excretion of glucose and help lower elevated blood glucose levels in patients with type 2 diabetes.
 
As a part of the risk management plans for empagliflozin and empagliflozin/metformin hydrochloride agreed upon by the European Medicines Agency (EMA), a post-authorisation safety study (PASS) will be performed to assess the risk of urinary tract malignancies in patients initiating empagliflozin, compared to patients initiating dipeptidyl peptidase-4 (DPP-4) inhibitors. Prior to the development of the protocol for this study, a feasibility assessment of three databases in Europe (Clinical Practice Research Datalink (CPRD) and data with potential for linkage (Hospital Episode Statistics (HES), and Office for National Statistics (ONS) mortality statistics) in the United Kingdom (UK) and the national registers in Sweden and Finland) was performed with the aim to detail the minimum data requirements for the study and to assess, for each potential data source, the data quality, completeness of recorded information for urinary tract malignancies, and possibility of linkage with cancer registries, mortality registries, and other data sources. Initially, this study included two countries, the UK (CPRD GOLD) and Sweden, with follow-up until 31st December, 2019. In order to increase the accumulated patient years and number of patients initiating the study drugs as well as accounting for the long latency period related to risk of malignancies, the study follow-up was first extended until 31st December, 2020 and Finnish national registers were included. In this version of the protocol (Version 7.0), CPRD Aurum was included and the study period extended to 31st December, 2021 for both CPRD databases, further increasing the sample size and accumulated person-years, and, consequently, increasing study power.
		

Name of company: Boehringer Ingelheim			
Name of the finished medicinal product: Jardiance®, Synjardy			
Name of active ingredient: Empagliflozin (A10BK03) Metformin and empagliflozin (A10BD20)			
Protocol date: 16-Sep-2015	Study number/ Document number: 1245.97 / c03856813-10	Version/Revision: 8.0	Version/Revision date: 17-May-2023
Research question and objectives:	
Research Question: The aim of the study is to assess the risk of urinary tract malignancies in patients initiating empagliflozin (free or fixed-dose combination) compared to patients initiating a DPP-4 inhibitor.
 
Primary objectives:
 
 (i) To estimate the adjusted hazard ratios (aHRs) and incidence rates (IRs) of all urinary tract cancers (bladder, renal and other urinary tract cancers) in patients initiating empagliflozin compared to patients initiating a DPP-4 inhibitor (ii) To estimate the aHRs and IRs of bladder cancer in patients initiating empagliflozin compared to patients initiating a DPP-4 inhibitor (iii) To estimate the aHRs and IRs of renal cancer in patients initiating empagliflozin compared to patients initiating a DPP-4 inhibitor 
Secondary objective: To estimate the aHRs and IRs of each primary outcome (all urinary tract cancers, bladder cancer, renal cancer) with respect to:
 
 a. increasing cumulative dosage of empagliflozin exposure b. dosage of empagliflozin prescribed per use (e.g., 10mg vs 25mg of empagliflozin) c. time since first dose of empagliflozin exposure 		

Name of company: Boehringer Ingelheim			
Name of the finished medicinal product: Jardiance®, Synjardy			
Name of active ingredient: Empagliflozin (A10BK03) Metformin and empagliflozin (A10BD20)			
Protocol date: 16-Sep-2015	Study number/ Document number: 1245.97 / c03856813-10	Version/Revision: 8.0	Version/Revision date: 17-May-2023
Study design:	
This is a non-interventional, comparative, cohort safety study based on European healthcare databases. The databases for this study are constructed from linked prescription, hospital, general practitioner, cancer and death registration records. The study will use an “incident users” design and compare new users of empagliflozin to new users of DPP-4 inhibitors. The index date will be defined as the date on which each identified new user receives the index prescription for empagliflozin, or a DPP-4 inhibitor. Follow-up will start 6 months after the index date (12 months in sensitivity analyses) to account for an empirical induction/promotion period. To minimize channelling bias, individuals will be matched with similar treatment and clinical history at index date by deriving propensity scores (PS). PS-matched cohorts will be derived for the comparison from the study base by matching patients who initiate empagliflozin with patients who initiate DPP-4 inhibitors at index date. To further gain power, the highest possible matching ratio in each country-level dataset will be used. This will be implemented using a variable ratio approach in all countries, where exposed patients are matched to as many control patients as possible, up to a maximum of 3 matched controls. Thus, an observational cohort is constructed to study the risk of urinary tract cancer among the two treatment groups. Depending on sample size, combination exposures with metformin will be accounted for through separate PS, stratification, or adjustment.
		

Name of company: Boehringer Ingelheim			
Name of the finished medicinal product: Jardiance®, Synjardy			
Name of active ingredient: Empagliflozin (A10BK03) Metformin and empagliflozin (A10BD20)			
Protocol date: 16-Sep-2015	Study number/ Document number: 1245.97 / c03856813-10	Version/Revision: 8.0	Version/Revision date: 17-May-2023
Population:	
The broad study population will include all patients from CPRD GOLD and CPRD Aurum in the UK and patients in the nationwide registers in Sweden and Finland, who have purchased at least one prescription of empagliflozin, or DPP-4 inhibitor drugs during the study period 2014-2020 (2021 for CPRD). Patients initiating empagliflozin, or DPP-4 inhibitor fixed-dose combinations with metformin will be included.
 
Index date: Date of first purchase/prescription of empagliflozin, or a DPP-4 inhibitor during follow-up (2014-2020; 2014-2021 for CPRD). Patients initiating DPP-4 inhibitor fixed-dose combinations with metformin will also be included.
 
The study population will be selected from the broad study population with the following inclusion and exclusion criteria:
 
Inclusion criteria:
 
 • Diagnosis of type 2 diabetes (T2D) • Age over 18 years at index date • At least 1 year of membership in the database prior to index date; in CPRD, at least 1 year of continuous up-to-standard registration in the CPRD prior to the index date 
Exclusion criteria:
 
 • Patients with any cancer (excluding non-melanoma skin cancer) prior to index date • Diagnosis of type 1 diabetes or other specific non-T2D • Use of any SGLT-2 inhibitor or any DPP-4 inhibitor (including free or fixed-dose combinations) prior to index date • Use of fixed-dose combinations of SGLT-2 inhibitors with DPP-4 inhibitors 
Diagnosis of end stage renal disease or receipt of renal dialysis prior to index date
		
Variables:	
Outcome variables:
 
 • All urinary tract cancers • Bladder cancer • Renal cancer 

		

Name of company: Boehringer Ingelheim			
Name of the finished medicinal product: Jardiance®, Synjardy			
Name of active ingredient: Empagliflozin (A10BK03) Metformin and empagliflozin (A10BD20)			
Protocol date: 16-Sep-2015	Study number/ Document number: 1245.97 / c03856813-10	Version/Revision: 8.0	Version/Revision date: 17-May-2023

Definition of exposure:
 
The primary definition of exposure for as-treated (AT) analysis is whether an individual is exposed to one of the following two index drug groups during the study period starting from 6 months after the index date and ending at treatment discontinuation of index drug:
 
 • Empagliflozin, or • DPP-4 inhibitor (sitagliptin, saxagliptin, linagliptin, vildagliptin, or alogliptin). 
Patients initiating empagliflozin, or DPP-4 inhibitor in fixed-dose combinations with metformin will be included. Note that use of any of these drugs prior to index date is an exclusion criterion.
 
Secondary definitions of exposure include
 
 • cumulative dosage of empagliflozin use, • daily dosage of empagliflozin prescribed per use (10mg vs 25 mg), and • time since first dose of empagliflozin. 
The following covariates, at a minimum, will be accounted for as variables for exact or PS matching and stratification, and in sensitivity analyses, in the risk set definition in nested-case-control (NCC) design and as covariates to derive inverse-probability of treatment weight (IPTW) in marginal structural models (MSMs) and/or model adjustment. These covariates will be identified based on codes recorded prior to the index date (exclusive of index date) unless otherwise specified below.
 
 • Socio-demographic variables (age, sex, year of index date, length of available look-back time) • Concomitant medications (insulin use, other oral glucose lowering medication use, diabetes treatment complexity, other non-diabetes medications) • Comorbidities such as 
 ◦ Diabetic complications (including latest HbA1c value) ◦ Urinary tract-related diseases ◦ Cardiovascular diseases • BMI, smoking, alcohol use (closest to index date) 
Additional covariates will be included according to data availability are, such as socioeconomic position and laboratory measurements.
			

Name of company: Boehringer Ingelheim			
Name of the finished medicinal product: Jardiance®, Synjardy			
Name of active ingredient: Empagliflozin (A10BK03) Metformin and empagliflozin (A10BD20)			
Protocol date: 16-Sep-2015	Study number/ Document number: 1245.97 / c03856813-10	Version/Revision: 8.0	Version/Revision date: 17-May-2023
Data sources:	
The following databases are country-specific data sources from which a linked master database for each country will be constructed.
 
The UK: CPRD GOLD and CPRD Aurum optionally complemented with HES (Outpatient data, and Admitted Patient Care data), and ONS mortality sources.
 
Sweden: The following nationwide population-based registers will be accessed: The National Patient Register, the Swedish Prescribed Drug Register, the Swedish Cancer Register, the Causes of Death Register, the National Diabetes Register, and the Longitudinal integration database for health insurance and labor market studies.
 
Finland: The following nationwide population-based registers will be accessed: the Finnish prescription register/the registry for reimbursed medications, the Care register for health care (HILMO), the Register of primary health care visits (AvoHILMO), and the Finnish cancer register. Additionally, four regional electronic medical record (EMR) databases will be accessed to obtain information on laboratory measures.
 
Initially, the country-level datasets will be analysed separately. Thereafter, country-level estimates will be pooled using meta-analysis techniques to gain power and produce as narrow confidence intervals (CI) as possible.
 
If patient numbers accumulating in these data sources are below the expected counts, alternatives will be evaluated as described in Section 8.4.4
		

Name of company: Boehringer Ingelheim			
Name of the finished medicinal product: Jardiance®, Synjardy			
Name of active ingredient: Empagliflozin (A10BK03) Metformin and empagliflozin (A10BD20)			
Protocol date: 16-Sep-2015	Study number/ Document number: 1245.97 / c03856813-10	Version/Revision: 8.0	Version/Revision date: 17-May-2023
Study size:	
The study size will be driven by the uptake of empagliflozin and DPP-4 inhibitors for the treatment of T2D to improve glycaemic control in adults in the UK, Sweden, and Finland. Study-size and power computations were carried out for the meta-analysis of the primary outcomes. Originally, it was expected that by the end of 2019, approximately 18,000 empagliflozin-treated patients will accumulate in the CPRD and Swedish databases. However, based on the conservative estimates from the third monitoring report (2019), the expected sample size was higher than anticipated with approximately 25,000 empagliflozin initiators eligible for inclusion in the study. Further, additional 38,000 patients were expected by the end of 2020 with the inclusion of Finnish databases, for a total of approximately 78,000 by the end of the study period. Updated estimates in the fifth interim report (2021) indicated that a total of 57,000 empagliflozin initiators were expected to be eligible for inclusion in the study in CPRD-GOLD, Sweden, and Finland by the end 2020. New estimations including the inclusion of CPRD-Aurum and the extension of the study period to the end of 2021 for both CPRD databases suggest that a total of 67,490 empagliflozin initiators could be eligible for inclusion across all three countries. Furthermore, the observed numbers of patients initiating DPP-4 inhibitors in each country suggest that achievable matching ratios would be 1:3 in UK-CPRD, 1:1 in Sweden, and 1:2 in Finland.
 
Power to detect relative risks of 1.5 and 2 was determined at the meta-analysis level, for each of the study outcomes, based on the expected number of individuals exposed to empagliflozin eligible for inclusion in the study for each country (approximately 16,887 in UK-CPRD (GOLD and Aurum), 32,334 in Sweden, and 18,269 in Finland) and the observed IRs of urinary tract cancers, bladder cancer and renal cancer in country-level study populations as reported in the fifth interim report (UK-CPRD: 111.5, 66.7, 26.5 per 100 000 PY; Sweden: 164.5, 104.1, 58.0 per 100 000 PY; Finland: 161.5, 86.8, 71.6 per 100 000 PY; respectively for urinary tract cancer, bladder cancer and renal cancer). Power calculations performed for the primary comparison between empagliflozin users and DPP-4 inhibitors indicated that the power at the meta-analysis level for detecting a hazard ratio of 1.5 would be 93.6% for urinary tract cancer and 84.0% for bladder cancer. Power for detecting a hazard ratio of 2.0 for renal cancer would be 97.0%.
		

Name of company: Boehringer Ingelheim			
Name of the finished medicinal product: Jardiance®, Synjardy			
Name of active ingredient: Empagliflozin (A10BK03) Metformin and empagliflozin (A10BD20)			
Protocol date: 16-Sep-2015	Study number/ Document number: 1245.97 / c03856813-10	Version/Revision: 8.0	Version/Revision date: 17-May-2023
In addition, anticipated study sample size would ensure sufficient power for the meta-analysis to detect the targeted effect size of < 1.6 for urinary tract cancers and bladder cancer and the targeted effect size of < 2.0 for renal cancer, with 80% power under the expected matching ratios in each study country. Results from the second and third interim analysis showed that not enough patients will have accumulated in the UK CPRD or Swedish registers by the planned end of data collection to reach the desired sample size. For this reason, the protocol was first amended to expand the study population by including data from the Finnish national registries and extend the study period until 31 st December 2020. Following results from the fifth interim analysis, the protocol was further amended to also include the CPRD Aurum database and to extend the study period to the end of 2021 for both CPRD databases.			

Name of company: Boehringer Ingelheim			
Name of the finished medicinal product: Jardiance®, Synjardy			
Name of active ingredient: Empagliflozin (A10BK03) Metformin and empagliflozin (A10BD20)			
Protocol date: 16-Sep-2015	Study number/ Document number: 1245.97 / c03856813-10	Version/Revision: 8.0	Version/Revision date: 17-May-2023
Data analysis:	
For the primary, secondary, and further objectives, the main data analysis will be conducted in two stages: (i) construction of the PS-matched cohort by modelling the exposure to empagliflozin vs. DPP-4 inhibitors and (ii) estimating the effect of exposure to empagliflozin on the urinary tract (bladder, renal and other) cancers using aHR compared to those exposed to DPP-4 inhibitor and their respective IRs. Additional sensitivity analyses will be performed to validate the robustness of alternative definitions of outcome, exposure, and covariates, to assess reduction of bias due to matching and presence of detection/diagnostic bias, and to evaluate the current use of empagliflozin exposure using an AT analysis. Patients starting a combination of empagliflozin, and metformin (whether a fixed-dose or free combination) will be compared with patients starting a combination of a DPP-4 inhibitor and metformin. Depending on sample size, combination exposures with metformin will be accounted for through separate PS, stratification, or adjustment.
 
IRs (crude and adjusted) will be presented for each exposure group and stratified by relevant variables using the Poisson regression approach. Relative risks will be presented as hazard ratios (HRs) adjusted for relevant variables using the Cox's model with the time- varying covariate approach. The aHRs and IRs will be presented along with 95% CIs for the risk estimates. Country-level estimates will be entered into meta-analysis models to compute pooled estimates.
		

Name of company: Boehringer Ingelheim			
Name of the finished medicinal product: Jardiance®, Synjardy			
Name of active ingredient: Empagliflozin (A10BK03) Metformin and empagliflozin (A10BD20)			
Protocol date: 16-Sep-2015	Study number/ Document number: 1245.97 / c03856813-10	Version/Revision: 8.0	Version/Revision date: 17-May-2023
Milestones:	Jardiance (empagliflozin) was granted EU marketing authorisation in May 2014. Launch in the UK and Finland was in August 2014; launch in Sweden took place November 2014. Synjardy (empagliflozin/metformin hydrochloride) was granted EU marketing authorisation in May 2015. Protocol version 1 was submitted to the EMA for review in September 2015, version 2 in February 2016, version 3 in June 2016, version 4 in March 2019, and protocol version 5.0 in Sep 2019. Registration in the EU PAS register occurred in December 2016 (EUPAS16424) and was updated following protocol endorsement by the EMA. The number of users in each treatment cohort have been monitored. Based on the available patient numbers and the event rates observed, a decision will be made to proceed with adjusted, treatment-stratified analyses at the interim report stage. Any decision based on the results of the interim reports concerning the length of the study period or the use of other data sources will be approved via a protocol amendment. Taking into account the database lags, the analysis of Swedish and Finnish data through December 2020 will be performed between Q3 2022 and Q3 2023. Analysis of CPRD data through December 2021 will be performed in Q3/Q4 2023 and the final report will be finalised by Q2 2024. Progress reports including monitoring of users in each data source were sent to EMA annually up to 2021.		

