8.4.3 Finnish data sources

An additional, feasible data source in Europe includes the national registers in Finland, which were evaluated in the feasibility assessment before this study.

As in Sweden, Finland has a well-developed population-wide register system with longitudinal follow-up data. The persons are identified in the registers with a unique PID and thus the records can be linked for research purposes on subject level between the registers. Further, the data obtained from registers can be linked with data obtained from the EMR databases.

The following Finnish nationwide data sources will be included: Care register for health care (HILMO), Register of primary health care visits (AvoHILMO), Special reimbursement register, Prescription register, Cause of death register, Cancer register, Population register centre, and Statistics Finland ([Table 5](#)). HILMO and AvoHILMO include diagnoses associated with healthcare encounters in specialized and primary care, respectively. The Special reimbursement register will be used for identification of chronic comorbidities. This register includes patients who are entitled for special refunds of medicine expenses based on their chronic conditions. The Finnish nationwide Prescription register contains information on outpatient medication purchases in pharmacies. The register contains information on all purchased prescribed medicines within the reimbursement scheme. Cause of death register includes time of death and the cause of death classified according to the ICD categorization. Cancer register includes information on all diagnosed cancers, details of the tumour, and description of treatment.

The study data will be extracted from these registers using the general process as described above for Sweden ([Section 8.4.2](#)). Information about highest level of education will be obtained as a proxy for socioeconomic status from Statistics Finland, and information on patient's place of residence and migration will be obtained from Population register centre.

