Further, to obtain data on important potential confounders, specifically BMI, blood pressure, smoking, and laboratory measures such as HbA1c and eGFR, EMR databases will also be included in the study. Four regional EMR databases (Helsinki, Espoo, Vantaa, and Helsinki University Hospital [HUS] area), covering both primary and secondary care in the capital area of Finland, will be contacted separately to obtain access to their data. The data obtained from different data sources will be linked as described previously ([Section 8.4.2](#)).

Permissions to use the data may be received upon providing a research plan to the authorities responsible for the registers. The protocol is also subjected to relevant Ethical Committee's review and approval. The data permit processes and timelines for data permit granting by the authorities responsible for the registers vary between different registers and countries, as well as the requirements for the local research collaboration and the publication of results [[R15-4861](#)].

In Finland, all the data will be delivered to and analysed in the remote access server environment provided by the national permit authority Findata. The data holders will extract the relevant data and deliver it to Findata for pseudonymization. Before data delivery to the

Findata server environment, the data holders will collect and manage data according to their own standards. After the data is delivered to the Findata server environment by the data holders, [REDACTED] will process the data.

[REDACTED] will use the study identification numbers for data linkage on individual level. [REDACTED] will have access to pseudonymized raw data without PINs. Therefore, the researchers at [REDACTED] will have access to data where individuals cannot be directly identified.

In Finland, the full study data including follow-up period until the end of 2020 will be available in June 2022.

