8.9.2 Generalizability

In the current study three population-based data sources (CPRD GOLD, CPRD Aurum, and Swedish and Finnish national registries) will be used. CPRD GOLD provides data entered by primary care practitioners in a routine clinical care setting and covers approximately 8.8% of

the UK population and CPRD Aurum about 13% of England population. The patients are broadly representative of the UK population in terms of age, sex and ethnicity. In Sweden, the national registries cover practically all patients with T2D. In Finland, the coverage of the EMR data is approximately 26.7%, and study population is broadly generalizable. Therefore, the study results can be generalized to similar patients with T2D in other geographic settings, including most industrialized countries.

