Estimated glomerular filtration rate (eGFR) at index date	
eGFR estimate derived from serum creatinine measurement using the CKD-Epi equation:
 $\text{eGFR (mL/min/1.73 m}^2\text{)} = 141 \times \min(\text{S}_{\text{cr}}/\text{K}, 1)^a \times \max(\text{S}_{\text{cr}}/\text{K}, 1)^{-1.209} \times 0.993^{\text{Age}} \times 1.018 \text{ [if female].}$ 
a = -0.329 (females) or -0.411 (males).
 
Evaluated at index using closest value to index date.
	
Time-fixed Continuous Categorical <15 (ml/min/1.73 m²) (kidney failure) 15-29 (ml/min/1.73 m²) (severely decreased) 30-44 (ml/min/1.73 m²) (Moderately to severely decreased) 45-59 (ml/min/1.73 m²) (Mildly to moderately decreased) 60-89 (ml/min/1.73 m²) (Mildly decreased) ≥90 (ml/min/1.73 m²) (Normal)
	
UK: CPRD Sweden: NDR Finland: EMR databases

Proprietary confidential information © 2024 Boehringer Ingelheim International GmbH or one or more of its affiliated companies

Renal impairment at index date	
The variable is evaluated at index date and indicates an eGFR < 60 (ml/min/1.73 m²) in all available history prior to index date.
 
Evaluated at index date using all available history prior to index date.
	
Time-fixed Categorical Yes No
	
UK: CPRD Sweden: NDR Finland: EMR databases

UTI or pyelonephritis	
The variable is initialized at index date and indicates a register record with a diagnosis of UTI or pyelonephritis using all available history. If no diagnosis prior to index date, it is time-updated to indicate any diagnosis of UTI or pyelonephritis after index date.
 
ICD-10 and READ diagnosis codes for UTI or pyelonephritis in Annex I.
 
Initialized at index and updating from index date onwards.
	
Time-dependent Categorical: Yes No
	
UK: CPRD Sweden: NPR Finland: HILMO, AvoHILMO

Liver disease at index date	
The variable is evaluated at index date and indicates a register record with a diagnosis of liver disease using all available history prior to index date.
 
ICD-10 and READ diagnosis codes for liver disease in Annex I.
 
Evaluated at index date using all available history prior to index date.
	
Time-fixed Categorical: Yes No
	
UK: CPRD Sweden: NPR Finland: HILMO, AvoHILMO

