9. MISSING DATA

A high frequency of missing values is not expected for most variables, with the possible exception of lifestyle and biological measurement variables. For the medical history conditions / comorbidities to be collected for inclusion in the propensity score, the absence of a code for a condition will be interpreted as an absence of the event.

If a variable is missing for only some of the patients, a missing data category will be added and utilized in the analysis. If a variable is missing for more than 50% of patients, removal of the variable from the relevant model or analysis (propensity score, multivariable Cox's regression, NCC matching) will be considered.

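### Finnish renal impairment comes only from capital-area EMR databases and is not supplemented by nationwide kidney diagnoses, so impairment short of end stage and not coded as diabetic nephropathy goes unadjusted in most Finnish patients

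*Protocol*

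**What the plan says.** Protocol Table 4 and Annex 6 list renal impairment as a propensity-score (PS) candidate, separately from eGFR. SAP Table 13 makes it a yes/no flag, fixed at index, that "indicates an eGFR < 60 (ml/min/1.73 m²) in all available history prior to index date". The source entry reads "Sweden: NDR Finland: EMR databases" after CPRD for the UK, so Finland has one source.

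The Protocol abstract introduces that source after the nationwide Finnish registers: "Additionally, four regional electronic medical record (EMR) databases will be accessed to obtain information on laboratory measures". Protocol 8.4.3 describes the four Finnish EMR databases as "covering both primary and secondary care in the capital area of Finland" and counts eGFR among the important potential confounders they are meant to supply. Protocol 8.9.2 adds: "In Finland, the coverage of the EMR data is approximately 26.7" per cent. It does not say of what.

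The nationwide registers are described in Protocol 8.4.3: "HILMO and AvoHILMO include diagnoses associated with healthcare encounters in specialized and primary care, respectively". The SAP already uses them in Finland for the end-stage renal disease and dialysis exclusion (Table 3) and for diabetic nephropathy (Table 12). Nephropathy is a PS candidate (6.5.1) and is balance-checked (6.6.2). In Table 13 itself, hypertension is a diagnosis or repeated raised blood pressure, and its Finnish sources are HILMO, AvoHILMO and the EMR databases together.

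SAP section 9 has three rules. An absent code for a medical-history condition counts as no event. A partly missing variable gets a missing category. The third reads: "If a variable is missing for more than 50% of patients, removal of the variable from the relevant model or analysis" will be considered. The SAP does not say which rule governs renal impairment.

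**The concern.** A covariate that the plan names as a PS candidate is measurable only where an EMR laboratory value exists, while diagnosis registers that cover the rest of Finland are already being extracted. Kidney function could plausibly influence the choice between the two drug groups, and two of the three primary outcomes include renal cancer.

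A gap in the PS also carries forward. The base model in SAP 6.7.2 adjusts only for unbalanced covariates among those in the PS, and the list of time-dependent variables for the adjusted model contains no measure of kidney function. If impairment is commoner among DPP-4 starters and raises recorded cancer, the Finnish HR is pulled downward, which is the unfavourable direction for a safety study.

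**Working it through.** **1. Reproducing the plan's power figures.** The documents give no pooled weights, so I first checked the inputs against Protocol Table 7 at HR 1.5. The inputs come from its footnotes (urinary tract / bladder / renal rates per 100,000 person-years):

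- Finland: N 18,269, ratio 1:2, follow-up 2.4 years, rates 161.5 / 86.8 / 71.6.
- Sweden: N 32,334, ratio 1:1, follow-up 2.2 years, rates 164.5 / 104.1 / 58.0.
- UK: N 16,360, ratio 1:3, follow-up 2.4 years, rates 111.5 / 66.7 / 26.5.

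Events per arm = n(1 − exp(−rate × time)), with follow-up shortened by the 0.5-year lag. Power = Φ(√(dk)·(HR−1)/(k·HR+1) − 1.96), where d is total events and k the allocation ratio (empagliflozin to DPP-4).

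For Finland, urinary tract: e1 = 83.9, e0 = 111.9, d = 195.8, k = 0.5. Then √97.9 × 0.5/1.75 − 1.96 = 0.87, so power is 80.7%.

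| | Recomputed | Stated |
|---|---|---|
| Finland | 80.7 / 54.5 / 47.0% | 80.6 / 54.3 / 46.7% |
| Sweden | 85.2 / 66.7 / 43.1% | 85.1 / 66.6 / 42.9% |
| UK | 67.1 / 45.9 / 21.5% | 63.7 / 43.1 / 20.3% |

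Finland and Sweden reproduce. The UK does not fit as closely, and step 2 allows for that.

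**2. Pooled weight.** Weight = 1/(1/e1 + 1/e0 + τ²). At HR 1.5, τ² = 0, renal cancer:

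- Finland 37.2 × 49.7/86.9 = 21.3
- Sweden 47.8 × 31.9/79.7 = 19.1
- UK 12.4 × 24.7/37.1 = 8.3

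Finland's share is about 44%. The same step gives 35% for urinary tract and 32% for bladder. I varied HR (1, 1.5, 2), τ² (0, 0.01, 0.05), the lag (applied or not) and UK N (16,360 or the abstract's 16,887), and also scaled UK information by 0.925 to approximate its stated power. Finland's share then ranges over 34–36% (urinary tract), 31–33% (bladder) and 39–44% (renal).

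**3. Who lacks the measure.** Assuming 26.7% applies to study patients, 0.267 × 18,269 = 4,878 empagliflozin initiators have an eGFR source and 13,391 (73.3%) do not. Finns outside the EMR area would carry 0.733 × 35.1 = 26%, 0.733 × 31.9 = 23% and 0.733 × 43.8 = 32% of the pooled weight.

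**4. The three rules, applied to those patients.**

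- Missing category: they share one level, so impaired and unimpaired patients are not distinguished.
- Removal considered: 73.3% exceeds 50%, so the variable may leave the model.
- Absence read as No: impaired patients are labelled unimpaired.

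None of these adjusts for their impairment.

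**5. Illustrative bias.** All inputs here are assumptions. With prevalence p1 in empagliflozin starters, p0 in DPP-4 starters and cancer risk ratio R, the HR outside the EMR area is multiplied by B = (1 + p1(R−1))/(1 + p0(R−1)), and the pooled HR by B raised to the step 3 weight.

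- Mild: 10% vs 20%, R = 1.3. B = 1.03/1.06 = 0.972; pooled 0.993 / 0.993 / 0.991.
- Strong: 10% vs 30%, R = 2. B = 1.1/1.3 = 0.846; pooled 0.958 / 0.962 / 0.948.

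**The case against.** The strongest reply is that Finland has considerable kidney-related control. Nephropathy is a nationwide PS candidate, end-stage disease and dialysis are excluded nationwide, and hypertension, heart failure, diuretics and diabetes duration also have nationwide sources. This stands. A reader might infer that kidney disease is largely uncontrolled in Finland, and the documents do not support that. The size of the remaining gap cannot be judged, because the code lists are separate files and it is not visible which kidney codes count as nephropathy.

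A reader might also infer that the balance check would hide an imbalance. Under the No default at 26.7% coverage, true prevalences of 13% vs 20% are recorded as 3.5% vs 5.3%. By the SAP 6.6.2 formula, the standardized difference falls from 18.9% to 9.1%, which passes the 10% rule. But 12% vs 20% is recorded as 3.2% vs 5.3%, or 10.6%, which does not pass. The default itself is the least natural reading, since the flag rests on a measurement rather than a code and section 9 expects missing values among biological measurements. Tripping the rule would still not help unmeasured patients, because adjusting for the flag leaves all of them at No.

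The channelling argument is thin. The eGFR threshold in Protocol section 6 concerns a dose increase, not the choice between drug groups, and the risk factors listed in Protocol 6.1 do not include renal impairment. Finally, SAP 6.7.3.2 will examine differences in data availability before pooling, so the limitation is partly anticipated. That review could prompt a change, but it does not specify one.

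**Conclusion.** The point holds in limited form. The single Finnish source, its regional reach and the unused nationwide diagnoses are all documented. If 26.7% describes study patients, most Finns receive no adjustment for impairment that is neither coded as diabetic nephropathy nor end-stage, whichever missing-data rule is applied, in a country with roughly a third or more of the pooled weight.

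The likely bias is small. The pooled factor of about 0.95–0.99 rests on assumed prevalences and risks, gives no credit to correlated covariates, and takes its direction from two conditions the documents do not establish. A reader might infer that a harm signal would be masked. At the strong end, the minimum detectable pooled renal HR of 1.62 in Protocol Table 9 would become 1.62 × 0.948 = 1.54, which is attenuation rather than concealment. This is a cheap improvement, not a flaw that undermines the primary result.

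**What to change.** In SAP Table 13, add for Finland a chronic kidney disease or renal failure diagnosis from HILMO or AvoHILMO at any time before index. Enter it in the Finnish PS and balance table. It is preferable as its own yes/no covariate, so that codes and eGFR are not mixed. The alternative is a combined eGFR-below-60-or-diagnosis flag, following the structure the SAP already uses for hypertension. Keep the EMR-based eGFR variable separate with a missing category, and state that an unmeasured eGFR is not read as No. Stating the denominator of the 26.7% in Protocol 8.9.2 would also help.

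The cost is one table row and a short ICD-10 list applied to registers already extracted. No stated sample size or power changes. The drawbacks are that diagnosis codes are less sensitive than eGFR and that the Finnish covariate set would differ somewhat from those of the UK and Sweden. The pre-pooling heterogeneity review should record that difference.
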